Those who decide to participate will be asked to attend a baseline visit prior to beginning their exercise programme to determine if they are suitable. The research project will be re-explained and questions encouraged. Following this, informed consent will be obtained if appropriate. A clause outlining the conduction of an interview, voice recording and use of anonymous quotes will be included in the consent form, but this will be optional. Patients will still be able to participate in the study without completing an interview.

Baseline and follow-up visits

Baseline and follow-up visits will be completed for all research participants who complete the full intervention timeframe (i.e. 6-8 weeks). Those choosing to discontinue the intervention before completing the full intervention timeframe will be withdrawn. Follow-up visits will be completed immediately following completion of the HIIT programme, and then 12-weeks post-intervention. An additional follow-up will also be completed 4-weeks post-intervention at the Hull site only.

[figure not shown]
Travel expenses for study visits (baseline and follow-ups) will be reimbursed. Patients can be reimbursed a maximum of £75 to cover the costs of transport/parking that may be accrued.

Patients will be asked not to eat a heavy meal or smoke for 3 hours before the visit and testing (18). Patients will also be asked to dress appropriately, especially in terms of footwear and instructed to avoid unusual physical activity efforts in the preceding 12 hours (18). As testing will not be performed for diagnostic purposes, patients will not be asked to withdraw or refrain from taking any medications (18). At each study visit, the patient's medical notes will be reviewed before assessment of current and past medical history. Patients will be asked questions relating to previous medical history including previous

diagnoses, current symptoms, and medications to determine the presence of any contraindications to exercise testing (18, 19).

Resting blood pressure and HR will then be taken followed by height, weight, body mass index (BMI), waist circumference, hip circumference and waist to hip ratio. During the baseline and subsequent visits, a number of objective physiological and subjective patient-level measures will be performed.

Trial Procedures

Measurement of primary and secondary endpoints

Primary endpoint – safety, utility and tolerability

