Safety will be determined by the occurrence of any adverse events (AE) or serious adverse events (SAE). In accordance with the GCP decision tree for adverse event reporting all events will be reported to the sponsor and recorded to determine the safety of the intervention.

Utility will include eligibility (n = eligible/screened), recruitment (recruited/eligible), and adherence (number of patients completing the HIIT programme). The number of patients screened, recruited and commencing the HIIT programmes will be monitored at each hospital site. A register (if required, i.e. more than one patient attending), will be taken at each exercise class to record patient adherence and the completeness of each session will be recorded (i.e. how many minutes the patient completed). It is estimated that all patients should complete 18 sessions in total within 6 weeks. However, where any sessions are missed, the intervention period can be extended to 8 weeks to allow these sessions to be added on. Those not completing 18 sessions over the extended 8-week period will be deemed to have satisfactorily completed the intervention as long as they have completed >80% of the intervention (i.e. ≥ 15 out of 18 sessions). All patients completing the allotted 6-8 weeks for the intervention (regardless of whether they have completed \geq or < 15 sessions) will still be followed up. Those choosing to discontinue the intervention before completing the full intervention timeframe will be withdrawn.

Tolerability will be assessed by identifying if patients are able to reach and maintain the prescribed training range required to perform HIIT, for each full interval. Heart rate (HR) data will be collected throughout each HIIT session and saved on an encrypted USB stick this will then be compared to the 85-100%HRMax training range that has been prescribed – to determine if patients are able to achieve it. This range will be in line with an ongoing HIIT trial in CAD at 85-90% peak power output (PPO), aiming to achieve >85%HRMax, derived from CPET (15). If patients are not able to achieve 85-100%, this will determine the suitability of this HIIT protocol in this population. Reasons for stopping the HIIT exercise sessions (e.g. leg pain), will be recorded.

Secondary endpoints

Acceptability

Acceptability will be assessed by patient feedback using semi-structured interviews.

conducted using a sample of patients in three groups:

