Group 1: Patients who are eligible for the study but decide not to participate (non-consenters). The interviews will explore reasons why patients chose not to participate in the

study and whether study material could be amended to be more appealing. Patients in this group will be signposted to the relevant interview section of the patient information sheet that they have already received. Those who agree to participate in an interview will sign an interview specific consent form.

Group 2: Those who agree to participate in, and complete, the exercise programme.

The interviews will explore patient's experiences of the HIIT programme, how easy/hard they found it, whether they enjoyed it and whether they would be willing to undertake it again. They will also be asked to provide any additional information related to potential problems/barriers to the programme and any changes they may feel are required.

Group 3: Those who agree to participate but discontinue after at least one session.

Patients will be asked the same initial questions as group 1, but they will be asked why they dropped out of the programme and what could have been changed to prevent them doing so.

An interview guide with a pre-determined set of open questions will be used but the interviews will be flexible to allow the interviewer to ask further probing questions based on patient responses. All interviews will be conducted face-to-face in a private room, recorded using a Dictaphone, transcribed verbatim and anonymised. Patients will be informed that they do not have to answer any questions that they feel uncomfortable with and all responses are confidential.

Clinical outcome measures:

Pain-free and maximal walking distance:

The test that will be used starts at 2mph and 0% grade, with grade increasing by 2% every two minutes whilst speed remains constant (20). This test will be used to determine PFWD and MWD at each study visit. A stopwatch will be started when the patient walks, they will indicate to the researcher when they begin to feel IC pain, which will be recorded as PFWD. The patient will continue to walk until the pain is too severe and they need to stop, this will be recorded as MWD.

Quality of life:

Two questionnaires will be used;

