The qualitative data will also be analysed using an inductive thematic analysis. Thematic analysis involves identifying, analysing and reporting themes that become apparent within the data (39). Themes collate important or patterned responses from within the data that are related to the research question (39). This means that as the researcher reads and re-reads the transcriptions, a pattern of responses will emerge that are related to the research question and can be grouped together under a theme heading. The approach will be inductive, which means that the themes are data-driven, thus emerging from the data, do not fit into a pre-existing coding frame and are not driven by the researcher's theoretical interest in the area (39).

In an attempt to minimise missing data from losses to follow-up patients will be contacted well in advance of their follow-up appointment and the researcher will attempt to rearrange any missed follow-ups. However, any missing data due to loss to follow-up will be recorded and reported adequately. Any missing data that should have been collected during a study visit will be investigated via source data and patient notes to exhaust all options. If data is still missing, it will be coded adequately during analysis and reported in results. Missing data will not be imputed by the researcher to avoid bias.

Safety reporting

Collecting and reporting data on adverse and serious adverse events will be in accordance with GCP and the Research Governance Framework v. 3.3, 2017.

Adverse events (AE)

An adverse event is any untoward occurrence that happens to a subject during the conduct of the study. The event may be as a result of the study conduct or intervention or there could be no relationship between the study and the AE at all.

Serious adverse events (SAE)

An AE is deemed serious if it:

- Results in death
- Is life-threatening (patient is at risk of death at the time of the event)
- Requires hospitalisation or prolongation of existing hospitalisation
- Results in persistent or significant disability or incapacity
- Consists of a congenital anomaly or birth defect

Hospitalisation that was planned before partaking in the study (i.e. elective surgery) should not be considered a SAE unless it has to be prolonged.

Reporting period:

The AE reporting period for each patient begins as soon as they have given informed consent for the trial and ends 30 days after their final study visit.

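### Patients who stop HIIT early have no scheduled adverse event enquiry after stopping, and the end of their reporting period is tied to a study visit that, read literally, is baseline

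*Combined protocol and SAP*

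**What the plan says.** All references are to the combined protocol and SAP.

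- **Reporting period (Safety reporting).** The AE period opens at informed consent, which is taken at the baseline visit, and "ends 30 days after their final study visit".
- **Baseline and follow-up visits.** "Baseline and follow-up visits will be completed for all research participants who complete the full intervention timeframe". Follow-ups fall directly after HIIT and 12 weeks after it. "An additional follow-up will also be completed 4-weeks post-intervention at the Hull site only".
- **Early stopping.** Both that section and the primary endpoint section say: "Those choosing to discontinue the intervention before completing the full intervention timeframe will be withdrawn". Trial exit adds that an AE or SAE preventing continuation also ends participation.
- **What a study visit is.** The reimbursement sentences gloss study visits as baseline and follow-ups. Potential risks/barriers to the patient puts their number at three or four and deals with exercise sessions separately.
- **How AEs are found.** Safety reporting schedules a general-health discussion at each study visit. Otherwise the researcher records an AE on learning of it. The same section expects most events to happen away from study activity and accepts that patients may not mention those they think unrelated.
- **Role of safety.** It is part of the primary endpoint: "all events will be reported to the sponsor and recorded to determine the safety of the intervention".
- **Contact after stopping.** The acceptability interviews are "conducted using a sample of patients in three groups", one of which is "Group 3: Those who agree to participate but discontinue after at least one session". They are optional: "Patients will still be able to participate in the study without completing an interview".

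**The concern.** The protocol gives its own reason for asking about AEs: events mostly occur elsewhere and are under-reported unless someone enquires. That reason applies at least as strongly to a patient who no longer attends. Yet the scheduled enquiry is attached to visits that early stoppers do not have, and so is the closing date of the AE period.

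The patients affected are not a random subset. They can include people who left because of an AE, or who were withdrawn because they came to meet an exclusion criterion. Safety is a primary endpoint, and the protocol says that the safety of HIIT in this population is not known. The analysis section summarises AE rates over all participants and does not plan to show observation time beside them. A reader of the results could not tell a stopper who had no later events from one who was never asked.

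**Working it through.** **1. Visit count, checked against the protocol's own figure.**
- Coventry: baseline + end of HIIT + 12 weeks = 3 visits.
- Hull: the same + 4 weeks = 4 visits.

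This reproduces the stated three or four, so the 18 exercise sessions are not study visits.

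**2. Scheduled AE enquiries after baseline.**
- Completers (anyone who stays for the 6-8 week timeframe, whatever the number of sessions): 3 - 1 = 2 at Coventry, 4 - 1 = 3 at Hull.
- Early stoppers: 1 - 1 = 0.

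**3. AE period remaining after the last HIIT session.** This is the like-for-like comparison, because the gap concerns events after HIIT.
- Completers: 12 × 7 + 30 = 84 + 30 = 114 days. This is the same for a 6-week or an 8-week programme.
- Early stoppers, literal reading: the final study visit is baseline (day 0), so the period closes on day 30. If the last session is on day *d* after baseline, 30 - *d* days remain. That is 30 days if *d* = 0, none if *d* = 30, and a closing date before the last session if *d* > 30.
- The last case is possible. The programme runs to day 6 × 7 = 42, or day 8 × 7 = 56 if extended, so 42 - 30 = 12 to 56 - 30 = 26 days of it lie beyond day 30.

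Step 3 takes the first session to be on the baseline day, because the protocol gives no interval. Any delay increases *d* and shortens what remains for the stopper; the completers' 114 days do not change.

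**4. If the last session is counted as the final study visit.** The stopper then has 30 days after that session. The number of enquiries after stopping is still 0.

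**5. Size of any bias.** The protocol gives no dropout rate and no AE rate, so the number of missed events cannot be calculated.

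**The case against.** **Recording does not depend on visits.** AEs are recorded whenever the researcher learns of them, and the analysis section excludes no data for poor adherence. This stands. Events at supervised sessions, including one that makes the patient stop, would be recorded and kept. A reader might infer from the day-30 closing date that events at sessions after day 30 are lost. The text does not support that: a patient still attending on day 30 has follow-up visits ahead, so the period is open at that time.

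**The final study visit could mean the scheduled one.** End of trial says that the last study visit for this study is 12 weeks after the intervention. That section defines when the trial closes, not each patient's AE period, but it does leave some doubt. On that reading the period is longer, and there is still no enquiry within it.

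**The contrast can be exaggerated.** A reader might set a whole AE period of 42 + 84 + 30 = 156 to 56 + 84 + 30 = 170 days for completers against 30 days for stoppers. Those totals include the treatment weeks, when sessions are supervised, and rest on the most adverse reading. The contrast of 114 days with at most 30 is the fair one.

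**Other contacts exist.** The interviews with early stoppers are optional, cover a sample and ask why the patient left. Source data lists AEs among the items to note after a visit or telephone call, but no call to stoppers is scheduled. Neither is an AE enquiry after stopping.

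**The study has one arm, and no planned comparison sets stoppers against completers.** The completion subgroup leaves out those who withdraw. This stands, so no between-group result is distorted. The overall AE summary is what could be incomplete.

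**Some material is not visible.** A figure beside the visit schedule and the decision tree for AE reporting could hold a withdrawal contact. The point rests on the readable text.

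**Conclusion.** The point holds as a gap in finding events after early stopping. The text schedules no AE enquiry for early stoppers once they stop, against two or three after baseline for completers. On the most literal reading, their AE period leaves at most 30 days after the last session, and may close before it, against 114 days after HIIT for completers.

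This assumes that study visits are baseline and follow-ups only, that HIIT starts on the baseline day, that visits are on time, and that the unseen figure adds no contact. The lack of an enquiry does not depend on how the final study visit is read; the 30-day limit does.

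A reader might go further and conclude that the reported AE rate will be too low by a material amount. The protocol does not support a statement of size. It gives no dropout or AE rate and does not say whether rates count patients or events, and a patient who leaves because of a known AE already counts as having had one. What can be said is that later events in stoppers could be missed on a primary endpoint. That is worth correcting because the correction is small.

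**What to change.** 1. In Reporting period, state: *The AE period runs from informed consent until 30 days after the later of the last study visit and the last HIIT session.* This removes the doubt about which visit is meant and prevents the period from closing before the last session.
2. For early stoppers who have not withdrawn consent to contact, add one AE telephone call or notes check about 30 days after the last session. That is when their period ends, so one contact covers it.
3. In the analysis section, report AEs separately for early stoppers and completers, with observation time. The periods will still differ: 30 days after HIIT against 114.

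The cost is a few calls or notes checks and some unrelated events collected. Contact after withdrawal may need a change of consent wording and an amendment reviewed by the ethics committee; the consent form could not be checked here. The change does not make follow-up equal. Stoppers are observed for less time after HIIT, and completers' last 30 days still have no scheduled enquiry.

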Appendix 1: Amendment history

Amendment No.	Protocol version no.	Date issued	Author(s) of changes	Details of changes made
